8.5.1.3 Pharmacokinetic and immunogenicity sampling for pembrolizumab

Blood samples for pembrolizumab PK and IG analysis will be collected for both capmatinib plus pembrolizumab arm and pembrolizumab alone arm as outlined in [Table 8-9](#). PK and IG samples will be collected also at the end of treatment visit and in the event of a clinically significant AE (such as infusion reaction/anaphylaxis) or if IG is suspected. After the cut-off for the primary analysis is reached, no additional PK and IG samples will be collected for the subjects still ongoing in the study.

Table 8-9 Pembrolizumab pharmacokinetic and immunogenicity blood collection log – obsolete upon approval of protocol amendment 03

[figure not shown]
Cycle	Day	Scheduled Time Point (h)	Analytes
1	1	Pre-dose ^a	PK/IG
2	1	Pre-dose ^a	PK/IG
3	1	Pre-dose ^a	PK/IG
6	1	Pre-dose ^a	PK/IG
Every 6 cycles after C6D1 until discontinuation of study treatment	1	Pre-dose ^a	PK/IG
EOT		anytime	PK/IG
30-day safety follow-up ^b		anytime	PK/IG
Unscheduled		anytime	PK/IG

^a Take samples immediately prior to infusion of pembrolizumab

[figure not shown]
^b For subjects who return to the site for safety follow up assessment

8.5.1.4 Analytical method

[figure not shown]
Pharmacokinetic samples for capmatinib will be quantified using validated LC/MS/MS assays. The assay to quantify and assess the pembrolizumab PK and IG will be a validated homogeneous ELISA (Enzyme-linked immunosorbent assay).

Final

Final

Final

9 Study discontinuation and completion

9.1 Discontinuation

9.1.1 Discontinuation of study treatment

Discontinuation of study treatment for a subject can be initiated by either the subject or the investigator.

The investigator must discontinue study treatment for a given subject if he/she believes that continuation would negatively impact the subject's well-being.

Study treatment must be discontinued under the following circumstances:

- Subject/guardian decision
- Any situation in which study participation might result in a safety risk to the subject.
- Pregnancy
- Death

Following approval of protocol amendment 03, in countries where pembrolizumab is approved and available for the study indication, subjects may be transitioned to commercial pembrolizumab and discontinued from the study.

If discontinuation of study treatment occurs, the investigator should make a reasonable effort to understand the primary reason for the subject's premature discontinuation of study treatment and record this information.

Subjects who discontinue study treatment or who decide they do not wish to participate in the study further should NOT be considered withdrawn from the study UNLESS they withdraw their consent (see withdraw of informed consent section). **Where possible, they should return for the assessments indicated** in the assessment schedule. If they fail to return for these assessments for unknown reasons, every effort (e.g. telephone, e-mail, letter) should be made to contact the subject/pre-designated contact as specified in the lost to follow-up section. This contact should preferably be done according to the study visit schedule.

If the subject cannot or is unwilling to attend any visit(s), the site staff should maintain regular telephone contact with the subject, or with a person pre-designated by the subject. This telephone contact should preferably be done according to the study visit schedule.

After study treatment discontinuation, at a minimum, in abbreviated visits, the following data should be collected at clinic visits or via telephone/email contact:

- new / concomitant treatments
- Adverse events/Serious adverse events.

The investigator must also contact the IRT to register the subject's discontinuation from study treatment of capmatinib. The discontinuation of pembrolizumab is not required to be recorded in IRT.

9.1.2 Withdrawal of informed consent

Subjects may voluntarily withdraw consent to participate in the study for any reason at any time. Withdrawal of consent occurs when a subject:

- Does not want to participate in the study anymore, and
- Does not allow further collection of personal data

In this situation, the investigator should make a reasonable effort (e.g. telephone, e-mail, letter) to understand the primary reason for the subject's decision to withdraw his/her consent and record this information.

Study treatment must be discontinued and no further assessments conducted, and the data that would have been collected at subsequent visits will be considered missing.

Further attempts to contact the subject are not allowed unless safety findings require communicating or follow-up.

All efforts should be made to complete the assessments prior to study withdrawal. A final evaluation at the time of the subject's study withdrawal should be made as detailed in the assessment table.

Novartis will continue to keep and use collected study information (including any data resulting from the analysis of a subject's samples until the time of withdrawal) according to applicable law.

For US and Japan: All biological samples not yet analyzed at the time of withdrawal may still be used for further testing/analysis in accordance with the terms of this protocol and of the informed consent form.

For EU and RoW: All biological samples not yet analyzed at the time of withdrawal will no longer be used, unless permitted by applicable law. They will be stored according to applicable legal requirements.

9.1.3 Lost to follow-up

For subjects whose status is unclear because they fail to appear for study visits without stating an intention to discontinue or withdraw, the investigator must show "due diligence" by documenting in the source documents steps taken to contact the subject, e.g. dates of telephone calls, registered letters, etc. A subject should not be considered as lost to follow-up until due diligence has been completed.

9.1.4 Early study termination by the sponsor

The study can be terminated by Novartis at any time.

Reasons for early termination:

- Unexpected, significant, or unacceptable safety risk to subjects enrolled in the study
- Decision based on recommendations from applicable board(s) after review of safety and efficacy data
- Discontinuation of study drug development

In taking the decision to terminate, Novartis will always consider subject welfare and safety. Should early termination be necessary, subjects must be seen as soon as possible (provide instruction for contacting the subject, when the subject should stop taking drug, when the subject should come in for a final visit) and treated as a prematurely withdrawn subject. The investigator may be informed of additional procedures to be followed in order to ensure that adequate consideration is given to the protection of the subject's interests. The investigator or sponsor depending on local regulation will be responsible for informing IRBs/IECs of the early termination of the trial.

9.2 Study completion and post-study treatment

9.2.1 End of study

Following the study enrollment halt, the end of the study is defined as the earliest occurrence of one of the following:

- discontinued study treatment and completed the safety FU or
- died or
- withdrawn consent or
- been lost to follow-up.

See [Section 12](#) Data Analysis and statistical methods for details of timing of the final reporting of data.

9.2.2 Follow up

9.2.2.1 Safety follow-up

All subjects receiving study treatment must have safety evaluations for 30 days after the last dose of study treatment. The 30 day safety follow-up can be done by telephone call or visit. Concomitant medications will be collected until the 30-day safety follow-up has been completed or the start of a new antineoplastic therapy, whichever occurs first. A PK and immunogenicity sample should be collected at the 30-day safety follow up visit as described in [Section 8.5.1](#). If the 30-day safety evaluation is conducted by phone, samples do not need to be collected.

Data collected should be added to the Adverse Events CRF, the antineoplastic therapies since discontinuation of study treatment CRF, the Concomitant Medications CRF and the PK/IG CRF. For female subjects of child bearing potential, pregnancy tests will be performed as outlined in [Section 8.4.3](#).

As of 04-Feb-2021, collection of PK and IG samples is terminated. Following approval of protocol amendment 03, antineoplastic therapies since discontinuation of study treatment will not be collected.

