Following approval of protocol amendment 03, the efficacy and safety assessments will be performed as per each institution's standard of care. The assessment schedule in [Table 8-2](#) will no longer be applicable and will be replaced by [Table 8-2b](#).

The Assessment Schedule ([Table 8-2](#)) lists all of the assessments when they are performed. All data obtained from these assessments must be supported in the subject's source documentation.

Subjects should be seen for all visits/assessments as outlined in the assessment schedule ([Table 8-2](#)) or as close to the designated day/time as possible. Missed or rescheduled visits should not lead to automatic discontinuation. Subjects who prematurely discontinue the study for any reason should be scheduled for a visit as soon as possible, at which time all of the assessments listed for the final visit will be performed. At this final visit, all dispensed investigational product should be reconciled, and the adverse event and concomitant medications recorded on the eCRF.

During the course of the study visits, test procedures should occur on schedule whenever possible as per allowable visit windows specified in [Table 8-1](#) below.

As per [Section 4.6](#), during a public health emergency as declared by local or regional authorities i.e. pandemic, epidemic or natural disaster that limits or prevents on-site study visits, alternative methods of providing continuing care may be implemented by the investigator as the situation dictates. If allowed by local Health Authority and depending on operational capabilities, phone calls or virtual contacts (e.g. tele consult) can replace on-site study visits, for the duration of the disruption until it is safe for the participant to visit the site again.

Table 8-1 Allowable visit windows

Visit name	Window
Screening	Day -28 to Day -1
Cycle 1 Day 1	Within 3 days after randomization in IRT
Day 1 of the subsequent cycles	± 4 Days
PK/IG/PD sampling	Refer to tables in Section 8.5.1
Tumor assessments	± 7 Days
EOT	≤ 7 Days after decision of discontinuation of study treatment
Safety follow up assessment	± 7 Days
Survival follow- up	± 14 Days

Table 8-2 Assessment Schedule – obsolete upon approval of protocol amendment 03

Period	Screening	Treatment								Follow-up		
Visit Name	Screening	Cycle 1	Cycle 2	Cycle 3	Cycle 4	Cycle 5	Cycle 6	Subsequent cycles (Up to 35 cycles)	EOT	Safety	Disease progression	Survival
Day	-28 to -1	1	1	1	1	1	1	1	-	30	-	Every 12 weeks

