Visit Name	Screening	Cycle 1	Cycle 2	Cycle 3	Cycle 4	Cycle 5	Cycle 6	Subsequent cycles (Up to 35 cycles)	EOT	Safety	Disease progression	Survival
Day	-28 to -1	1	1	1	1	1	1	1	-	30	-	Every 12 weeks
Capmatinib												
Antineoplastic therapies since discontinuation of study treatment										X		
Survival follow up												X

X = assessment to be recorded in the clinical database or received electronically from a vendor

S = assessment to be recorded in the source documentation only

1. Only applicable for subjects with local PD-L1 TPS data available for study eligibility. The PD-L1 TPS data tested locally should be recorded in eCRF

2. Within 72 hours prior to first dose of study treatment

6. Only the first eight subjects enrolled into the treatment arm with capmatinib need to take the intensive PK samples specified in [Table 8-7](#). Refer to [Table 8-8](#) for the rest of subjects.

7. If subjects experience an SAE or AE leading to the discontinuation of the study treatment, an unscheduled PK blood sample should be obtained whenever possible

8. Only when subjects who return to the site for safety follow up assessment

Final

Table 8-2b Assessment Schedule – applicable upon approval of protocol amendment 03

Visit Name	Treatment Phase - all cycles until end of study treatment or 35 cycles	EOT	30-Day Safety Follow-up
Adverse Events	X (continuous)		
Concomitant Medications	X (continuous, until 30 days after last dose of study treatment or start of new antineoplastic medication, whichever is sooner)		
Study drug administration pembrolizumab	X (day 1 of every cycle)		
X = assessment to be recorded in the clinical database			

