All adverse events must be treated appropriately. Treatment may include one or more of the following:

- Dose not changed
- Dose reduced/increased
- Drug interrupted/withdrawn

6. its outcome

If the event worsens, the event should be reported a second time in the eCRF noting the start date when the event worsens in toxicity. For grade 3 and 4 AEs only, if improvement to a lower grade is determined, a new entry for this event should be reported in the eCRF noting the start date when the event improved from having been Grade 3 or Grade 4.

Conditions that were already present at the time of informed consent should be recorded in medical history of the subject.

Adverse events (including lab abnormalities that constitute AEs) should be described using a diagnosis whenever possible, rather than individual underlying signs and symptoms.

Adverse event monitoring should be continued for at least 30 days following the last dose of study treatment.

Once an AE is detected, it must be followed until its resolution or until it is judged to be permanent (e.g. continuing at the end of the study), and assessments must be made at each visit (or more frequently, if necessary) of any changes in severity, the suspected relationship to the interventions required to treat it, and the outcome.

Progression of malignancy (including fatal outcomes), if documented by use of appropriate method (for example, as per RECIST 1.1 criteria for solid tumors), should not be reported as a serious adverse event. However, if the progression of malignancy is considered to be related to study treatment as per Investigator's assessment and meets the SAE definition, the event should be reported as a serious adverse event.

Adverse events separate from the progression of malignancy (i.e. deep vein thrombosis at the time of progression or hemoptysis concurrent with finding of disease progression) will be reported as per usual guidelines used for such events with proper attribution regarding relatedness to the drug.

Information about adverse drug reactions for the investigational drug can be found in the capmatinib Investigator's Brochure or the locally approved package insert of pembrolizumab.

Abnormal laboratory values or test results constitute adverse events only if they fulfill at least one of the following criteria:

- they induce clinical signs or symptoms
- they are considered clinically significant
- they require therapy

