2.1.1.5 On-treatment assessment/event and observation periods

For all safety reporting the overall observation period will be divided into three mutually exclusive segments:

- **pre-treatment period:** from day of subject's informed consent to the day before first administration of study treatment
- **on-treatment period:** from date of first administration of study treatment to 30 days after date of last administration of study treatment (including start and stop dates)
- **post-treatment period:** starting at Day 31 after last administration of study treatment.

If dates are incomplete in a way that clear assignment to pre-, on-, post-treatment period cannot be made, then the respective data will be assigned to the on-treatment period.

Safety summaries (tables, figures) include only data from the on-treatment period with the exception of baseline data which will also be summarized where appropriate (e.g., change from baseline summaries). In addition, a separate summary for death including on-treatment and post-treatment deaths will be provided. In particular, summary tables for AEs will summarize only on-treatment events, with a start date during the on-treatment period (treatment-emergent AEs).

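### The ±7-day window on the 30-day safety follow-up conflicts with the duty to capture adverse events through Day 30, and an early in-window contact can be read as completing follow-up

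*Protocol*

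**What the plan says.** Several passages fix the end of safety observation at 30 days after the last dose:

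- Protocol 9.2.2.1: treated subjects "must have safety evaluations for 30 days after the last dose of study treatment".
- Protocol 10.1.1: "Adverse event monitoring should be continued for at least 30 days following the last dose of study treatment".
- Protocol 10.1.3: every SAE up to the same point is reportable, whatever its cause.
- SAP 2.1.1.5: the on-treatment period runs "from date of first administration of study treatment to 30 days after date of last administration of study treatment". Protocol 12.5.2 defines it in the same way.

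Other passages govern the contact at which those data are collected:

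- Table 8-2b, the schedule in force under Amendment 03, has one post-treatment column after EOT, the "30-Day Safety Follow-up". Its AE row is marked as continuous.
- Section 9.2.2.1 allows it to be remote: "The 30 day safety follow-up can be done by telephone call or visit".
- Table 8-1 gives the row for "Safety follow up assessment" a window of plus or minus 7 days. Tables 8-2, 8-3, 8-4 and 8-6 are labelled obsolete or no longer mandated under Amendment 03. Table 8-1 carries no such label.
- Section 9.2.1 takes the earliest of four events as the end of study. The first reads "discontinued study treatment and completed the safety FU or". It does not say on which day the follow-up counts as completed.
- Sections 9.2.2.2 and 9.2.2.3 remove progression and survival follow-up under Amendment 03.

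**The concern.** The window is symmetric, but the requirement it serves is a minimum. A contact can ask only about events up to the day it takes place. If it takes place before Day 30, it cannot establish what happened on the remaining days of the period that both documents treat as on-treatment. Section 9.2.1 then allows the subject to be closed, and the schedule offers no further occasion to ask.

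Completeness of the AE, SAE and on-treatment death summaries is at stake. SAP 2.8.1 reports the number and percentage of subjects with at least one event, and SAP 2.1 takes the subjects in the relevant population as denominator. A subject whose late event was never learned of stays in the denominator and counts as event-free. Under Amendment 03, AEs are among the few data still entered in the eCRF. At 15-Mar-2021, 50 subjects were still on treatment, so for them this contact lay ahead.

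**Working it through.** The plan gives no figure to reproduce. The check is day arithmetic, followed by a comparison of the rules.

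**Inputs.** Nominal contact: Day 30 after last dose (Table 8-2b; 9.2.2.1). Window: ±7 days (Table 8-1). Required observation: through Day 30 (9.2.2.1, 10.1.1, 10.1.3; SAP 2.1.1.5). Day 0 is the day of the last dose.

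**Range of in-window contacts.** Earliest 30 − 7 = Day 23; latest 30 + 7 = Day 37.

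**Days without scheduled ascertainment** after a contact on Day c: max(0, 30 − c).

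- c = 23: 7 days (Days 24 to 30)
- c = 26: 4 days
- c = 29: 1 day
- c = 30 to 37: 0 days

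**Share of the post-dose period at the maximum.** 7/30 = 23.3%, or 7/31 = 22.6% if the dosing day is counted.

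**Share of the whole on-treatment period at the maximum.** With k pembrolizumab doses exactly 21 days apart (an assumption: no delays), the period is 21(k − 1) + 31 days.

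- k = 1: 7/31 = 22.6%
- k = 4: 7/94 = 7.4%
- k = 10: 7/220 = 3.2%
- k = 35: 7/745 = 0.9%

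**Does another rule supply a contact on or after Day 30?**

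- Section 10.1.3 runs its 24-hour clock from when the site learns of the SAE. It creates no occasion to learn of one.
- The rule in 10.1.1 that an AE be followed to resolution applies to events already detected.
- Section 9.1.1 requires AEs and new treatments to be collected after discontinuation, by visit, telephone or email, preferably following the visit schedule. That schedule has no visit after the safety follow-up.

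None of these adds a scheduled contact after an early call.

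**Can *completed* act as a data stop?** Section 9.2.2.1 ends concomitant medication collection when the safety follow-up has been completed, while Table 8-2b ends it 30 days after the last dose. Both also stop at a new antineoplastic therapy. The two stopping points differ whenever the contact is early, so the protocol itself treats completion as a date that can close data collection.

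**With a 0/+7-day window.** Contacts fall on Days 30 to 37, and max(0, 30 − c) = 0 throughout.

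**The case against.** The strongest reply is that the window governs when the contact happens, not how long AEs are collected. Sections 9.2.2.1, 10.1.1 and 10.1.3 bind the site through Day 30, and Table 8-2b marks AE collection as continuous. On that reading the safety follow-up is not complete until 30 days have run, and a site that closes a subject on Day 23 breaches the protocol. This stands to the extent that a reader who infers that the protocol permits AE collection to stop on Day 23 goes too far. It does not remove the conflict. A site can satisfy Table 8-1 and the wording of 9.2.1 and still fall short of 9.2.2.1 and 10.1.1, and no passage says how the remaining days are covered.

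Three further objections also limit the point:

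- **Enrolment halt.** A reader might infer that the gap weakens the evidence on the tolerability problem that stopped enrolment. The documents do not support this. Capmatinib was stopped immediately after the halt on 21-Jan-2021, and the 50 subjects ongoing on 15-Mar-2021, 53 days later (10 + 28 + 15), were on pembrolizumab alone. Their final post-dose week says little about the combination.
- **Bias between arms.** A reader might infer this too. The window is the same in both arms, and nothing shows that early contacts are more frequent in one.
- **Size.** A total of lost subject-days would need a distribution of contact days, which the documents do not give, and the planned AE tables count subjects rather than person-time. A missed event changes a table mainly when it is the subject's first of its kind or a higher grade.

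It is also fair to say that the removed survival calls, made every 12 weeks for survival status and new therapies, would have caught late deaths but not AEs in general. Their removal adds little to the problem.

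**Conclusion.** The point holds as an internal inconsistency. The visit window in Table 8-1 and the undefined completion in 9.2.1 do not fit the Day 30 duties in 9.2.2.1, 10.1.1 and 10.1.3, or the on-treatment period in Protocol 12.5.2 and SAP 2.1.1.5.

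The firm size is a per-subject maximum of 7 of 30 post-dose days, reached only when the contact is on Day 23 and the site makes no later one. The gap shrinks to 1 day for a contact on Day 29 and is nil from Day 30. The direction is under-ascertainment. The documents give neither the number of early contacts nor the event rate on Days 24 to 30, so the effect on AE incidence cannot be computed, and no difference between arms is shown. The case for acting is that the repair is very cheap and removes the gap completely.

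**What to change.** Reconcile the passages by either or both of these changes:

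1. In Table 8-1, change the safety follow-up window from ±7 days to 0/+7 days, that is Days 30 to 37 after the last dose.
2. In Section 9.2.1, state that the safety follow-up is completed only by a contact on or after Day 30, with telephone allowed as in 9.2.2.1. If the first contact was earlier, one repeat call on or after Day 30 is needed before the subject is closed.

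The second change is sufficient alone and leaves Table 8-1 as it is. At the same time, align the end of concomitant medication collection in 9.2.2.1 with Table 8-2b. The on-treatment definition in the SAP needs no change. The cost is one table cell and/or one clause, and in practice slightly less scheduling flexibility or one extra telephone call for a subject contacted early.
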